8.1 Dermatologic Effects

Phototoxic reactions including severe edema, erythema, painful acral blistering, burning, and peeling of skin may occur with methoxsalen and conventional UV light. In addition, PUVA therapy has produced marked hyperpigmentation and, with high cumulative doses, photoageing of skin.

8.2 Phototoxic reactions to methoxsalen occur most commonly when the skin is overexposed to UV light or when dosage is excessive. Severe burns may occur if treated skin is accidentally exposed to additional UV light. Pruritus occurs in about 10% of patients treated with PUVA therapy utilizing methoxsalen.

8.3 Other adverse dermatologic effects associated with PUVA therapy include skin freckling, hypopigmentation, uneven or excessive tanning, dry skin, vesiculation and bullae formation, generalized exfoliation, nonspecific rash, urticaria, miliaria, folliculitis, acneiform eruption, aggravation or extension of disease, cutaneous tenderness, severe skin pain (lasting 1—2 months), onycholysis, pigmentation of the nails, and exacerbation of latent photosensitive dermatoses (e.g., lupus erythematosus).

8.4 Gastrointestinal (GI) Effects

Nausea is the most common adverse effect of oral methoxsalen, occurring in about 10% of patients. Nausea and other adverse GI effects may be minimized by administering 8-MOP with milk or food.

8.5 Central Nervous System (CNS) Effects

Dizziness and headache can occur with PUVA therapy utilizing methoxsalen.

8.6 Other Adverse Effects

PUVA therapy may also damage the eyes and may increase the risk of cataract. To reduce these side effects eye shields will be used during irradiation and UV protective glasses are required for 24 hours after ingestion of 8-MOP.

Cheilitis and transient loss of muscle coordination reportedly occurred in patients receiving oral methoxsalen.

Although abnormal liver function test results were reported in a few patients receiving oral methoxsalen, this observation has not been confirmed by others and a causal relationship has not been established. Edema, malaise, leg cramps, and hypotension occurred with PUVA therapy utilizing methoxsalen.

9. Premature Termination

9.1 Drop-out

Drop-out of single study participants may be due to

- withdrawal of informed consent
- intolerable adverse events
- violation of the study protocol
- emergence of an exclusion criterion
- emergence of concomitant disease
- pregnancy
- any other circumstance that would endanger health of the proband with continued study participation

9.2 Discontinuation of the study

The investigator may discontinue the study anytime in the interest of the probands if severe adverse events or other unforeseen problems occur.

Ethics Committees concerned and competent authorities should be informed about premature discontinuation and its reason within 15 days.

10. Monitoring

Monitoring will be performed according to the monitoring plan of this study. The investigator will cooperate with the monitor and provide unrestricted access to source data and all other study materials.

The investigator will keep detailed records in the patient charts on study visits, distribution of study drugs, test results, concomitant diseases, and adverse events. The monitor will regularly verify entries on the CRFs with source data and check compliance with the study protocol and continuous data entry. The monitor will handle all data confidentially to ensure integrity and privacy of the study participants.

11. Data protection

Recording and analysis of personal data within this clinical trial will be performed according to applicable data protection laws, provided the study participant has consented to this prior to enrolment. Informed consent will include information on data protection as follows:

1. Data collected within this clinical trial will be recorded on case report forms, handled in a strictly confidential way.
2. If necessary for evaluation of the clinical trial, authorized personnel of the sponsor, of competent authorities and/or Ethics Committees may confidentially review personal data of the study participants at the trial site.

3. The study participant will be informed that participation in the clinical trial may be terminated at any time without giving a reason and without any consecutive disadvantage. However, due to legal requirements, inspection of personal data by authorized persons may be continued in a confidential manner.

12. Clinical evaluation and laboratory tests

Patients with histopathologically documented MF and clinical stage IA to II B, who have given informed consent and are willing to participate in the study should undergo the following testing and investigation:

12.1. Before treatment start - Pretreatment evaluation (see also Appendix: Table 4: Summary of visits and assessments) (Within 28 days before treatment start):

- Medical history and clinical examination (if clinically palpable lymph nodes: lymph nodes ultrasounds); in case of ultrasonic suspicion of disease-specific lymph node involvement a lymph node biopsy and/or excision will be done
- Determination of mSWAT
- Skin biopsies for diagnostic purposes and for determination of cytokine levels as well as T-cell receptor rearrangement (TCR-R)
 - All standard study biopsies should be taken from the site of the marker lesion (defined at baseline). Biopsies should only be taken from other parts of the body (outside the area of the marker lesion) if the response at that site is clinically ambiguous.
- Ophthalmologic examination
- Laboratory tests: Hematology (hemoglobin, WBC with differential and platelet counts), serum biochemistry: serum AST (SGOT), ALT (SGPT), alkaline phosphatase, urea, creatinine, and glucose
- Antinuclear antibodies (dsDNA, Ro/SSA, La/SSB)
- Blood draw for cytokine, TCR-R and FOXP3 mRNA analysis and Cell free DNA BCT for blood tumor cell analysis (see Appendix: Table 5)
- Pregnancy test (for women with childbearing potential) in blood or urine
- Photographic documentation
- DLQI (Dermatology Life Quality Index)
- HADS (Hospital Anxiety and Depression Scale)

12.2. During treatment and in the follow-up period:

Assessments will be done, as described in Appendix Table 4 at specific time points. A biopsy after the start of PUVA therapy (e.g. scheduled at week 6 with a gray period of 2 weeks) should be taken on a day of PUVA treatment before UVA exposure.

For control purposes blood samples from a maximum of 30 healthy control subjects and 30 samples of normal skin available from other studies will be analyzed, together with the samples of this study.

13. Statistics

Previous studies have shown that MF lesions reappear after a very variable time interval with median 9 to 15 months, depending on the study [WACKERNAGEL]. PUVA maintenance therapy intends to prolong this lesion-free interval and to reduce recurrence rate after discontinuation of the maintenance therapy.

Appendix Figure 2: Overview of treatment effects. All patients get standard PUVA therapy. After remission patients are assigned either to controls or to nine months of maintenance therapy. The treatment effect is the extension of the median time to recurrence (black double arrow). This comes along with lower risk of recurrence (Curve (1) is higher than curve (2)). Some patients suffer from recurrence during maintenance therapy, i.e., the tilt in the straight line segment of curve (1) from month 3 to month 12. The secondary end point refers to time to recurrence after finishing treatments successfully (dashed curves (3) and (4), dashed arrow). Curve (3) gives the survival function after maintenance treatment conditional on being free from lesions after therapy. Curve (4) is a shifted version of curve (1) in order to align the survival functions for comparison.

13.1. Study design

A randomized placebo controlled clinical trial with 3 to 6 months of PUVA therapy as control and 3 to 6 months PUVA plus 9 months of PUVA maintenance therapy as index therapy. In the Appendix Figure 1 the time-dependent probability of recurrence (“Survival function”) is given for 4 settings.

The primary endpoint of the study is the comparison of median time to recurrence after complete remission between study arm A and study arm B (comparison of curve (1) vs. curve (2), Appendix: Figure 2). A secondary endpoint is the comparison of time from end of treatment to recurrence on condition that the patient is in remission at the end of treatment comparing study arm A and B (end of treatment in study arm A, month 12 to 15; end of treatment in study arm B, month 3 to month 6). This amounts to the comparison between curve (3) and curve (4). After the accrual period patients are observed until the closing date of the study for the main statistical outcome analysis. Patients who have not experienced recurrence by the closing date are considered as censored. Treatment groups are compared by survival analysis (logrank test).

13. 2. Sample size calculations and study duration

Sample sizes were calculated with nQuery Advisor 4.0 software (www.statistical-solutions-software.com). The assumptions were $\alpha=0.05$, $\text{power}=0.8$, one(two)-sided logrank test and an accrual time of 2 years.

According to an earlier study at the dermatologic clinic the median time to recurrence after PUVA therapy was 1 year. An exponential survival function with parameter $\lambda_1=0.7$ was chosen for controls, giving a median time to recurrence of 1 year.

The alternative hypothesis (i.e. the minimum clinically relevant treatment effect) was chosen to be exponential with $\lambda_2=0.35$ (relative hazard 2, median time to recurrence 2 years) for the primary treatment effect. The overall duration of the study (to enrol 55 patients assuming an accrual period of 2 years) until closing date for the main statistical outcome analysis was assumed to be four years (accrual phase, 24 months; initial PUVA treatment of last patient enrolled, 3 months; PUVA maintenance treatment in last patient enrolled, 9 months; minimum follow-up period, 12 months). Scenario D1 and D4 refer to these assumptions. Independent of the closing date for the main statistical outcome analysis the maximum follow-up in an individual patient will be 60 months.

| | Primary endpoint | | | | Secondary endpoint | | | |
|---|------------------|-----------|-----------|-----------|--------------------|-----------|-----------|-----------|
| | D1 | D2 | D3 | D4 | D5 | D6 | D7 | D8 |
| Test significance level | 0.05 | 0.05 | 0.05 | 0.05 | 0.05 | 0.05 | 0.05 | 0.05 |
| 1 or 2 sided test? | 2 | 1 | 2 | 1 | 2 | 1 | 2 | 2 |
| Length of accrual period | 2 | 2 | 3 | 3 | 2 | 2 | 3 | 3 |
| Maximum follow up | 3.75 | 3.75 | 4.75 | 4.75 | 3 | 3 | 4 | 4 |
| Control hazard λ_1 | 0.7 | 0.7 | 0.7 | 0.7 | 0.7 | 0.7 | 0.7 | 0.7 |
| Maintenance hazard λ_2 | 0.35 | 0.35 | 0.35 | 0.35 | 0.35 | 0.35 | 0.35 | 0.35 |
| Hazard ratio, $h=\lambda_1 / \lambda_2$ | 2 | 2 | 2 | 2 | 2 | 2 | 2 | 2 |
| Power (%) | 80 | 80 | 80 | 80 | 72 | 73 | 74 | 76 |
| n per group | 47 | 37 | 44 | 35 | 47 | 37 | 44 | 35 |
| Accrual per year (2 Treatments) | 48 | 38 | 32 | 26 | 48 | 38 | 32 | 26 |

For the secondary endpoint (recurrence after 9 months of maintenance therapy vs. recurrence after standard therapy only) essentially the same scenario was assumed: exponential survival, hazard ratio 2. Only the length of follow up was shortened by 0.75 years. In this regard not power but sample size was fixed and the power was variable. Scenario D5 to D8 relate to these assumptions.

Finally scenario D2 was chosen. 37 patients per group are required (41 patients if accounting for 10% loss to drop-out, non-compliance and/or follow-up).

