1.1. Prognosis

Most prognostic factors in MF include type and extent of skin involvement and presence or absence of extracutaneous disease, which determine clinical stage (Appendix: Table 1). Recent findings suggest that patient's life expectancy is not adversely affected in stage I A (limited patch, papules and/or plaques covering <10% of the skin surface), while patients diagnosed with tumor disease or erythroderma (stages IIB-IVB) have a worse overall outcome, with median survival of 4 to 5 years [WILLEMZE].

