3.2. Secondary endpoints

- Comparison of time from end of treatment to recurrence on condition that the patient is in complete remission at the end of treatment between patients treated with maintenance therapy vs. patients without maintenance therapy.
- Cytokine response in serum and tissue
- Quality of life
- HADS

4. Patient selection criteria

4.1. Inclusion Criteria:

- Histopathologically documented MF clinical stage IA-IIB (see Table1) confirmed by current or previous diagnostic lesion biopsy
- A Karnofsky performance score ≥ 60 (see Table 2)
- Age ≥ 18 years - ≤ 85
- Anti-ds-DNA (antinuclear antibodies) AND anti-Ro/La antibodies: negative
- Acceptable organ function defined as follows:

SGOT (AST) and SGPT (ALT) ≤ 2.5 times the upper limit of normal for the institution

- Creatinine ≤ 2 times the upper limit of normal for the institution
- No evidence of severe cardiac insufficiency (NYHA grade III-IV)
- Women of child bearing potential must have a negative serum or urine pregnancy test (β -HCG) within seven (7) days prior to randomization
- Absence of any serious intercurrent illness or infection at time of entry into the study that could interfere with planned treatment
- Patients must be willing to accept limiting sun exposure on the day receiving PUVA treatment
- Written informed consent

4.2. Exclusion criteria:

- Pregnancy and Lactation
- Photosensitive diseases such as lupus erythematosus or basal cell nevus syndrome
- Skin cancer syndromes such as Xeroderma pigmentosum or basal cell nevus syndrome
- PUVA (oral or topical) treatment within the last 3 months

5. PUVA treatment and follow-up

Psoralens are photosensitising agents. Methoxsalen – the most commonly used drug is a psoralen derivative that is structurally and pharmacologically related to trioxsalen. For PUVA treatment 8-methoxypsoralen (8-MOP) will be used. Patients receive a liquid preparation of 8-MOP (10 mg) in soft gelatine capsules (Oxsoralen®; Gerot Pharmazeutika GmbH, Vienna, Austria, please refer to the Summary of Product Characteristics). The dose of 8-MOP is based on the patient's weight. The standard dose of approximately 10 mg per 20 kg body weight will be given 1 h before UVA exposure, according to the following table:

| Body weight (kg) | 8-MOP (Oxsoralen) dose (10mg = 1 Cps) mg = Cps |
|-------------------------|---|
| < 30 | 10 = 1 |
| 30 - 50 | 20 = 2 |
| 51 - 65 | 30 = 3 |
| 66 - 80 | 40 = 4 |
| 81 - 90 | 50 = 5 |
| 91 - 115 | 60 = 6 |
| > 115 | 70 = 7 |

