| mild (+) | loss of appetite without alteration in eating habits |
| moderate (++) | oral intake decreased without significant weight loss, dehydration or malnutrition |
| severe (+++) | inadequate oral caloric or fluid intake |

Vomiting:

| | |
|---------------|--------------------------|
| none (-) | |
| mild (+) | 1 episode in 24 hours |
| moderate (++) | 2-5 episodes in 24 hours |
| severe (+++) | ≥ 6 episodes in 24 hours |

After 12 weeks of treatment or thereafter at week 16, 20 or 24 (after 24, 32, 40, or 48 PUVA treatments, respectively) patients with complete remission will be randomized by a computer generated list for treatment allocation into two arms (arm A and B, see below). Patients who haven't experienced complete remission after 24 weeks will discontinue active study participation and will enter an observatory study arm.

Patients with complete response will be randomized to receive either PUVA-maintenance therapy (arm A) or no maintenance therapy (arm B) (Figure 1)

Arm A: oral 8-MOP+UVA

Patients will be treated with PUVA maintenance therapy at constant single UVA doses (UVA-dose will be the same as given in the last treatment session in week 12, 16, 20 or 24 of PUVA therapy). Maintenance treatment will be given once a week for one month (4 weeks), every 2 weeks for 2 months (8 weeks) and after three months once a month over 6 months (Appendix: Figure 1). After 9 (10, 11, or 12) months of maintenance therapy (14 treatments) patients will discontinue therapy. If PUVA treatment does lead to erythema during maintenance therapy, the dose for the next treatment will be reduced by up to 30%.

Patients with recurrence during PUVA maintenance will discontinue the study. After the end of maintenance therapy the patients will be followed up every three months in the first year after treatment, every 6 months in the second year and once a year from year 3 to 5 or until recurrence of the disease.

Arm B: control arm – Patients will receive no therapy. Patients are followed up at the same intervals like patients in study arm A (Appendix: Table 4).

Observatory patient arm:

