Patients who did not response completely to therapy after a maximum of 24 weeks or 48 PUVA treatments and patients with recurrent disease (see section 7) after complete response will enter an observatory arm. Treatment of these patients will be entirely in the discretion of the treating physician. These patients will have follow-up visit at month 12 after stop of PUVA treatment or at time point of recurrence to record patient history and clinical status.

6. Definition of response

The extent of the cutaneous involvement of the disease will be determined before start of PUVA treatment and monitored during and after treatment by assessing the modified severity-weighted assessment tool (mSWAT) [STEVENS]. mSWAT is an objective, quantitative, severity-weighted method to assess the extent of CTCL lesions (Appendix: Table 3).

Quantitative tool to assess disease burden in CTCL [STEVENS]:

The body is divided into 12 regions with preassigned %TBSA based on methodology used to assess burns. The extent of skin disease is assessed for each region and quantified by using the patient's palm as a "ruler" to measure the %TBSA involvement within each region:

- Patient's palm with 4 fingers, excluding the thumb and measured from wrist to fingertips, is 1% of TBSA.
- Patient's palm without fingers is 0.5% of TBSA.

mSWAT Score calculation: Sum of %TBSA from all body regions affected by patches X severity-weighting factor of 1 + Sum of %TBSA from all body regions affected by plaques X severity-weighting factor of 2 + Sum of %TBSA from all body regions affected by tumors X severity-weighting factor of 4 (Appendix: Table 3).

Specific skin lesions will be differentiated in:

Patches: flat lesions with a diameter larger than 1 cm

Plaques: elevated/palpable lesions with increased consistency with a diameter larger than 1 cm

Tumors: nodular lesions with the longest diameter larger than 1 cm.

Response will be determined as follows:

- Complete clinical response: Complete clinical disappearance of all cutaneous MF lesions compared to baseline mSWAT. (Clinically evident postlesional erythema and/or pigmentation will not be considered as persistent disease. It will be recorded but will not affect mSWAT.) If there is clinical doubt of complete remission, a diagnostic biopsy should be performed.
- Partial response (PR): more or at least 50% reduction in mSWAT

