- Stable disease (SD): less than 50 % reduction (from baseline) and less than 25 % increase of skin disease (compared with the smallest mSWAT since treatment started)
- Progressive disease (PD): more than 25 % increase in mSWAT compared with the smallest mSWAT since treatment started.

7. Definition of recurrence

Recurrence will be defined as re-occurrence of cutaneous disease, as determined by mSWAT at any time point (Complete remission = 100% clearing of skin disease (mSWAT of 0); recurrence is reappearance of skin lesions (mSWAT \geq 1)) [OLSEN (b)]: . If there is clinical doubt of continuous remission, a biopsy should be performed.

8. Adverse Events

Definitions

Adverse Event (AE)

Any untoward medical occurrence in a patient or clinical investigation subject administered a pharmaceutical product and which does not necessarily have a causal relationship with this treatment. An adverse event (AE) can therefore be any unfavourable and unintended sign (including an abnormal laboratory finding), symptom, or disease temporally associated with the use of a medicinal (investigational) product, whether or not related to the medicinal (investigational) product (see note for guidance on Clinical Safety Data Management: Definitions and Standards for Expedited Reporting).

Serious Adverse Event (SAE), Serious Adverse Drug Reaction (Serious ADR)

Any untoward medical occurrence that at any dose:

- results in death,
- is life-threatening,
- requires inpatient hospitalisation or prolongation of existing hospitalisation,
- results in persistent or significant disability/incapacity,

or

- is a congenital anomaly/birth defect

Suspected unexpected serious adverse drug reactions (SUSARs)

Suspected Unexpected Serious Adverse Drug Reactions (SUSARs) are side effects (probably or definitely connected with the administration of the investigational product), the nature or severity of which are inconsistent with the information available about the product. Information about the trial product contained in the SmPC (Summary of medicinal Product Characteristics) should be used to verify if the adverse reaction has been previously described.

Safety reporting

Investigator:

The investigator is responsible for reporting AEs, SAEs and SUSARs to the sponsor.

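### The planned unadjusted logrank is valid; prespecifying one primary Cox score test adjusted for entry stage, with Efron ties, is a cheap optional gain that pays only if stage predicts recurrence

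*Combined protocol and SAP*

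**What the plan says.** **Test.** Section 13.1: "Treatment groups are compared by survival analysis (logrank test". No covariate, stratified test or Cox model is planned. Section 13.3 describes computerised randomisation without strata.

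**Design.** Section 13.2 adopts scenario D2: one-sided 5%, 80% power, 37 per group, accrual 2 years, maximum follow-up 3.75 years, exponential hazards of 0.7 (control) and 0.35 (maintenance) per year.

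**Stage.** Section 4.1 admits "Histopathologically documented MF clinical stage IA-IIB". Section 6 adds: "The extent of the cutaneous involvement of the disease will be determined before start of PUVA treatment". On prognosis, section 1.1 says "Most prognostic factors in MF include type and extent of skin involvement and presence or absence of extracutaneous disease". It adds that "life expectancy is not adversely affected in stage I A" and that "patients diagnosed with tumor disease or erythroderma (stages IIB-IVB) have a worse overall outcome". It does not place IB or IIA.

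**Who is randomised.** Section 5: "patients with complete remission will be randomized by a computer generated list for treatment allocation into two arms". Section 7: "Complete remission = 100% clearing of skin disease (mSWAT of 0". Every randomised patient therefore starts with cleared skin.

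**Timing of recurrence.** Section 7 defines recurrence by mSWAT. Table 4 schedules mSWAT about 4, 12, 24 and 36 weeks after randomisation, then every three months, every six months and yearly, at the same intervals in both arms.

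**The concern.** The trial is small, with about 54 expected events and little margin over 80% power. A baseline factor that the protocol itself calls prognostic goes unused in both allocation and analysis. Without strata, the arms can differ in stage by chance. Under simple randomisation (assumed) with one third of patients IB-IIB, the SD of the between-arm difference in share is √(2 × 1/3 × 2/3 / 37) ≈ 0.11, or 11 percentage points.

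If stage predicts recurrence, adjustment recovers power without more patients. It is credible only if the covariate, the test and the tie rule are fixed beforehand. What is at stake is efficiency, not validity.

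**Working it through.** **1. Reproduce D2.** With uniform accrual A = 2 and total time T = 3.75, the event probability is 1 − [exp(−λ(T−A)) − exp(−λT)]/(λA).
- λ = 0.7: 1 − (0.2938 − 0.0724)/1.4 = 0.842.
- λ = 0.35: 1 − (0.5420 − 0.2692)/0.7 = 0.610.
- Expected events: 37 × (0.8419 + 0.6102) = 53.7.
- Schoenfeld power: Φ(√53.7 × ln 2 / 2 − 1.645) = Φ(0.895) = 81.5%.

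Standard formulas give 36 (Schoenfeld) to 39 (Freedman) per group, so the stated 37 reproduces.

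**2. Gain with untied event times.** The stage share and the stage hazard ratio are assumptions. Stage-specific curves were chosen so that each arm stays exactly exponential at 0.7 and 0.35, as the protocol writes it: p·s^r + (1−p)·s = exp(−λt), where p is the share in the worse group, r the stage hazard ratio and s the survival of the better group. Each case had 300,000 null and 100,000 alternative runs. Unadjusted power is about 81% in every case. The change with the Cox score test, in points, size-adjusted (nominal level in brackets), is:

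| Share in worse group | r = 1 | r = 1.5 | r = 2 | r = 3 |
|---|---|---|---|---|
| 50% | −0.7 (−0.2) | +0.6 (+1.1) | +3.0 (+3.6) | +8.6 (+8.7) |
| 30% | −0.7 (−0.2) | +0.5 (+1.0) | +2.4 (+2.9) | +6.7 (+6.9) |
| 20% | −0.7 (−0.3) | +0.1 (+0.6) | +1.8 (+2.2) | +5.0 (+5.2) |
| 10% | −0.7 (−0.3) | −0.2 (+0.1) | +0.7 (+0.9) | +2.3 (+2.5) |

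Null rejection was 5.1-5.3% for the logrank and 5.2-5.4% for the Cox score test; a smaller check gave up to 5.5% for the latter. At r = 2 and a 30-50% share the gain is worth 8-10% more information: 0.08 × 37 ≈ 3 to 0.10 × 37 ≈ 4 patients per arm. A stratified logrank was weaker than the Cox score test in every case.

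**3. Which share is relevant.** Only complete responders are randomised. If a share s of enrolled patients is IB-IIB and their response rate is k times that of IA, the randomised share is sk/(sk + 1 − s). With k = 0.5 (assumed), s = 0.3 gives 0.15/0.85 = 18% and s = 0.5 gives 0.25/0.75 = 33%. The 20% and 30% rows are therefore the ones to read.

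**4. Tied event times.** Recurrence was then dated at the next scheduled visit (30% share, nominal one-sided power):

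| r | Runs | Logrank | Efron | Breslow |
|---|---|---|---|---|
| 1 | 2,500 | 80.1% | 80.0% | 76.6% |
| 2 | 2,500 | 77.9% | 81.4% | 77.9% |
| 3 | 2,500 | 79.9% | 87.0% | 84.2% |

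The simulation error is √(0.8 × 0.2/2,500) ≈ 0.8 point per entry. A separate run of 4,000 gave the same picture. At r = 1, Breslow had 74.6% against 78.6% for the logrank, and Efron 78.3% against 78.4%. Breslow size was 3.6-4.0%.

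Efron thus keeps the gains of step 2. Breslow is conservative, costs 3.5-4.0 points at r = 1 and removes the gain at r = 2. It also does not reduce to the logrank when the covariate is uninformative, because its variance lacks the logrank's (n−d)/(n−1) factor for ties.

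**The case against.** The strongest case is that nothing is broken. Section 1.1 ties stage to life expectancy and overall outcome, not to recurrence after remission. Everyone starts at mSWAT 0, and both inputs to the gain are assumed. This stands, and it makes the change optional.

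Further points, and what remains of each:
- **Ties.** With heavy ties, an adjusted test without a tie rule could lose 3-4 points. This stands, so Efron must be named.
- **Covariate.** The IA vs IB-IIB cut is a pragmatic choice. IIA includes T1 disease, so the cut does not follow skin extent exactly. Section 12.1 and Table 4 do not list stage as a recorded item, and section 4.1 allows a previous biopsy. What stands is that the plan must say stage at study entry and have it recorded. Eligibility already requires it to be known.
- **Estimand.** Sections 3.1 and 13.1 compare medians by arm, which is a marginal contrast. Reporting the medians and the unadjusted logrank alongside answers this.
- **Cost.** Section 14 sends amendments to the competent authority and ethics committees. Arm B is untreated, so treating staff see recurrences by arm, and the timing of the change must be documented. Both stand.

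In the other direction, a reader might infer that the planned logrank is underpowered or invalid. The documents do not support that: at the protocol's arm-level hazards it keeps about 81% power. Only if the hazard ratio of 2 is read as holding within stage does its power fall (76.9% at r = 2 and 70.7% at r = 3, 30% share), and the protocol does not write it that way.

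**Conclusion.** This is an optional improvement, not the repair of an error. The unadjusted logrank is valid for the primary randomised comparison and matches D2. Nothing here concerns the secondary comparison, which is conditional on remission at the end of treatment.

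With 20-30% of randomised patients in the worse group, adjustment with Efron ties gains about nothing up to a stage hazard ratio of 1.5, about 2-3 points at 2 and about 5-7 at 3. If stage does not predict recurrence, it costs under about 1 point. The simulated one-sided size is about 5.2-5.5%, slightly above nominal.

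The result rests on an assumed stage mix, an assumed stage hazard ratio and the protocol's exponential hazards. A reader might take the +8.6 points in the table as the expected benefit. That figure needs a hazard ratio of 3 and a 50% share, above the 18-33% that selection of complete responders gives under the stated assumptions. Nor does section 1.1 show that stage predicts recurrence; that is plausible but undocumented.

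**What to change.** By amendment, before outcome data are examined by arm, add to section 13.1:
- The primary test is a Cox score test for treatment, at D2's level and sidedness, with one binary covariate: clinical stage at study entry before PUVA, IA vs IB-IIB, described as a pragmatic cut.
- Ties are handled by Efron's method.
- If one stage level is empty, the planned unadjusted logrank is used.
- The unadjusted logrank and the Kaplan-Meier medians by arm are reported alongside, and the adjusted hazard ratio is described as conditional on stage.
- No other covariate or test may become primary.

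Document the date of the change and that no outcomes by arm had been examined. If they already have been, leave the logrank primary and show the adjusted test as supportive only.

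**Cost.** A protocol amendment, which needs prior approval under section 14 if it is substantial; an explicit record of stage at entry; under about 1 point of power if stage is not prognostic; and a one-sided size of about 5.2-5.5%. No extra patients, visits or tests are needed.

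### The side and alpha of the final primary logrank test are not stated: the sample size rests on a one-sided 0.05 test, and a two-sided 0.05 test at 37 per group would have about 70% power

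*Combined protocol and SAP*

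**What the plan says.** - **Analysis (13.1).** "Treatment groups are compared by survival analysis (logrank test" is the whole specification of the primary comparison. Patients without recurrence at the closing date are censored. No side and no significance level are given.
- **Sizing assumptions (13.2).** Alpha 0.05, power 0.8 and a "one(two)-sided logrank test and an accrual time of 2 years". The section later says that its assumptions correspond to scenarios D1 and D4.
- **Scenario table (13.2), first four columns, D1 to D4.** The side row reads "1 or 2 sided test? | 2 | 1 | 2 | 1", the alpha row "Test significance level | 0.05 | 0.05 | 0.05 | 0.05" and the power row "Power (%) | 80 | 80 | 80 | 80". D1 (two-sided) needs 47 per group and D2 (one-sided) needs 37. Both assume two years of accrual and 3.75 years of maximum follow-up.
- **Choice (13.2).** "Finally scenario D2 was chosen. 37 patients per group are required", or 41 per group after a 10% allowance for losses.

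The documents give no reason for one-sided testing and do not say that the final primary test will be one-sided.

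**The concern.** The sample size and the analysis have to refer to the same test. Here the sizing is one-sided at 0.05, while the analysis text is silent. Two things follow.

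First, the success criterion can be read in two ways. A result favouring maintenance with a two-sided p-value between 0.05 and 0.10 is a success if D2's test is carried into the analysis, and a failure if the bare logrank test is taken as two-sided at 0.05. The two readings allow different false-positive rates in favour of maintenance: 5% and 2.5%. If the side is settled only after the data are seen, it cannot be defended as pre-specified.

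Second, the 80% power belongs to the one-sided test only. If the analysis is run two-sided at 0.05, the trial has less power than the target in 13.2.

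**Working it through.** **Inputs, all from 13.2.** Control hazard λ1 = 0.7 and maintenance hazard λ2 = 0.35 per year (ratio 2); uniform accrual over R = 2 years; maximum follow-up T = 3.75 years; equal groups; alpha 0.05. Uniform accrual is my assumption. The plan assumes exponential times.

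**Step 1: expected events.** With exponential times, P(event) = 1 − [exp(−λ(T−R)) − exp(−λT)] / (λR).

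- Control: 1 − (0.2938 − 0.0724)/1.4 = 0.842
- Maintenance: 1 − (0.5420 − 0.2692)/0.7 = 0.610
- 37 per group: 37 × 0.842 + 37 × 0.610 = 31.2 + 22.6, or 53.7 events before rounding (√d = 7.33)

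**Step 2: reproduce the plan's figures.** Three standard formulas were used, with z = 1.645 one-sided and 1.960 two-sided:

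- Freedman: power = Φ(√d × (2−1)/(2+1) − z)
- Schoenfeld: power = Φ(√d × ln 2 / 2 − z)
- Lachin-Foulkes, on the difference in exponential hazards: power = Φ{[√(2n)(λ1−λ2) − z√(4φ(λ̄))] / √(2φ(λ1)+2φ(λ2))}, where n is the number per group, φ(λ) = λ²/P(event) and λ̄ = 0.525

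A logrank simulation with 20,000 runs served as a check.

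| | Freedman | Lachin-Foulkes | Schoenfeld | Simulation | Plan |
|---|---|---|---|---|---|
| D2, n per group for 80%, one-sided | 38.3 | 37.8 | 35.4 | – | 37 |
| D1, n per group for 80%, two-sided | 48.6 | 47.9 | 45.0 | – | 47 |
| Power at 37, one-sided 0.05 | 78.8% | 79.3% | 81.5% | 80.7% | 80% |

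Both scenarios reproduce.

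**Step 3: the same 37 per group, two-sided at 0.05.**

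- Freedman: Φ(7.33/3 − 1.960) = Φ(0.483) = 68.6%
- Lachin-Foulkes: 69.5%
- Schoenfeld: Φ(7.33 × 0.3466 − 1.960) = Φ(0.580) = 71.9%
- Simulation: 71.0%

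If all 41 per group are evaluable (59.5 events), two-sided power is 73.0% (Freedman), 73.8% (Lachin-Foulkes) or 76.2% (Schoenfeld and simulation). With T = 4.0 in place of 3.75, 37 per group gives 70.3% to 73.6%. None of these reaches 80%.

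**Step 4: what the choice of side does to the threshold.** With about 54 events and a standard error for the log hazard ratio of about 2/√d, the smallest significant observed control-to-maintenance hazard ratio is:

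- one-sided 0.05: exp(2 × 1.645/7.33) = 1.57
- two-sided 0.05: exp(2 × 1.960/7.33) = 1.71

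An observed ratio between about 1.57 and 1.71 passes one test and fails the other.

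**Step 5: does the text of 13.2 settle it?** D1 is two-sided and D4 one-sided, and D4 assumes three years of accrual, although the paragraph states two. If D1 and D2 were meant, which would match the two-year accrual, the sentence would still name one scenario of each kind. Only the choice of D2 points one way, and it is a statement about sample size.

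**The case against.** The best defence is that the plan is open about what it did. The phrase in 13.2 lists inputs for a family of scenarios, some one-sided and some two-sided. The table labels each column and sets 47 beside 37, and then D2 is chosen. The direction is also visible elsewhere: the objective in section 2 asks whether maintenance prolongs disease-free survival, and the alternative hypothesis is a single value favouring maintenance. A one-sided test fits that, and nothing in the documents requires a 2.5% one-sided level.

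Most of this stands. A reader might infer that the plan claims 80% power for a two-sided test at 37 per group, or that it overstates its power. The documents do not support that: D2 is labelled one-sided and the two-sided requirement is printed next to it. Nor does 13.2 say that the final test will be done both ways; its wording describes the sizing. A declared one-sided design would be legitimate.

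What the defence does not reach is the analysis. Choosing a sample-size scenario does not set a decision rule, and the sentence in 13.1 that should set it gives neither side nor alpha. The primary endpoint is worded as a comparison between arms, which implies no direction, and the reference to D1 and D4 weakens the inference from D2.

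Section 13.2 also speaks of enrolling 55 patients, which matches neither 74 (2 × 37) nor 82 (2 × 41). That is a separate inconsistency, and settling the side of the test will not remove it.

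**Conclusion.** The concern holds as a gap in the analysis specification with a consequence for power. The sizing is one-sided at 0.05 and its arithmetic is sound, but the side and alpha of the final primary test are not fixed. The open region is a two-sided p-value between 0.05 and 0.10 favouring maintenance, roughly an observed hazard ratio of 1.57 to 1.71 at 54 events. If the final test is two-sided at 0.05, power at 37 per group is about 69% to 72% against the stated target of 80%, or 73% to 76% with 41 evaluable per group.

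These figures rest on the plan's own hazards, accrual and follow-up, on exponential times and uniform accrual, and on no losses among the patients counted. The spread within each range comes from the choice of formula. The plan's D1 figure of 47 per group shows the same gap without any recalculation.

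**What to change.** Before the outcome data are analysed:

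1. In 13.1, state the side and the alpha of the primary logrank test.
2. In 13.2, say which scenario the assumptions refer to, and reconcile the mention of D1 and D4 with the choice of D2. The table may keep its two-sided columns.
3. If D2 stands, state one-sided alpha 0.05, note that this is the same threshold as two-sided 0.10 in the direction of benefit, and disclose that two-sided 0.05 power at 37 per group is about 70%.
4. If a two-sided 0.05 test is intended, restate power at 37 per group as about 70% in place of 80%. Keeping the 80% target with that test would mean the plan's own D1: 47 per group, or 94 against 74 in total before losses.

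Items 1 to 3, and the restatement in item 4, change wording only. The price is either a less favourable stated power or an openly looser threshold.
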